1.1 SYNOPSIS

Clinical Trial Protocol Number	2019-0910
Title	Phase II study of neoadjuvant immune checkpoint blockade-based therapy with M7824 (bifunctional anti-PD-L1/ TGF- β Trap fusion protein) for untreated stage I-IIIA non-small cell lung cancers amenable for surgical resection
Trial Phase	II
IND Number	146722
Coordinating Investigator	[name], PhD The University of Texas – MD Anderson Cancer Center Houston, TX USA
Sponsor	The University of Texas – MD Anderson Cancer Center, Houston, TX
Trial center/country	Single institution trial / United States
Planned trial period (first subject in-last subject out)	TBD
Trial Registry	Pending NCT identifier
Endpoints: Primary Endpoints: To evaluate the rate of major pathologic response, defined as $\leq 10\%$ viable tumor cells in the resected specimen using the methods described by Pataer et al. in patients treated with induction M7824 monotherapy.	
Secondary Endpoints: To estimate: Toxicity (assessed by the NCI CTCAE v. 5) Peri-operative morbidity and mortality Response rates to induction treatment (by RECIST version 1.1) (1) Recurrence-free survival and Overall survival Survival rates at 12, 18 and 24 months To correlate major pathologic response with recurrence-free and overall survival Complete resection (R0) rate Pathologic complete response (pCR) in resected tumor specimens	

To correlate response assessed by imaging studies with outcomes (both major pathologic response to treatment and long-term recurrence-free survival)

CD8+ TILs in resected tumor tissues of patients treated with M7824

Exploratory Endpoints:

PD-L1 expression in tumor tissue

Multi-region next generation DNA and/or RNA sequencing in tumor tissue (including whole exome and/or whole genome sequencing) and in blood/normal tissue, so that tumor heterogeneity and mutational load can be correlated with efficacy of immunotherapy and/or other correlative markers

Immunophenotyping or characterization of the immune cell subsets in tumor tissue, including markers of T cell exhaustion, T cell activation, T regulatory cells, T cell function, antigen presenting cells, as well as CD20, Ki67, granzyme B, IFN- γ , TGF-beta, GATA-3, RORgt, BCL2, as well as CD68 and other markers relevant to immune profiling

Expression of immunoregulatory and co-stimulatory markers in TILs by flow cytometry, including, but not limited to, PD1, CTLA4, LAG3, 41BB, and TCR zeta chain

RNA and protein expression in tumor and adjacent normal tissue, including assessment of immune/inflammatory pathways

Immunophenotyping or characterization of the immune cell subsets in the periphery, including, but not limited to, T cells, B cells, NK cells, or subpopulations of the aforementioned immune cell types

Single cell genomics in tumor (including tumor positive nodes) and adjacent normal tissue

Serum soluble factors, including IFN-gamma and interferon inducible factors (such as CXCL9 and CXCL10), PD-L1, PD-1, anti-tumor antibodies, microRNAs (such as miR-513, and miR19b), IL-12, TNF α , IL-10, TGF- β , VEGF, IL-6, IL-8, IL-17, IL-18, C-reactive protein and, as well as other cytokines, chemokines, inflammatory factors and immune mediators

T cell receptor repertoire (TCR) sequencing in tumor tissue, adjacent normal lung and the periphery (pre- and post-neoadjuvant therapy)

Next generation sequencing of cell-free circulating DNA

Immunopeptidome analysis

Enteric microbiome analysis

CT imaging analysis.

[figure not shown]
Methodology and design:

This is an open label, phase 2 study with modular design assessing the experimental agent M7824 in the neoadjuvant setting. We will start investigating M7824 monotherapy (Arm A) induction treatment in patients with resectable NSCLC, with the primary objective to estimate the MPR in each arm. After confirmation of eligibility criteria, patients will be enrolled in Arm A. Sequential arms investigating induction M7824-based strategies may be added after completion of enrollment in Arm A (23 patients) based on emerging data with a protocol amendment

Planned number of subjects: Arm A: 23

Investigational Medicinal Product: M7824 Dose/mode of administration/ dosing schedule: M7824 will be administered intravenously at a dose of 1200 mg every 14 days (+/- 3 days).

Planned trial and treatment duration per subject: Subjects will receive M7824 monotherapy for three doses prior to surgery. Administration will be stopped due to documented progressive disease, unacceptable toxicity, consent withdrawal, or any criterion for withdrawal as outlined in this protocol.


Statistical methods The study is a phase II trial with a modular design. Currently, eligible patients will be accrued to the M7824 monotherapy (Arm A). The primary objective is to evaluate the rate of MPR, rather than hypothesis testing with pre-specified null and alternative MPR rates. There will be no interim futility nor efficacy monitoring. A sample size of 23 patients is proposed for the study. With an estimated accrual rate of approximately 2 patients a month, the accrual period is approximately 15-24 months.

Analysis of primary endpoint of major pathologic response (MPR): The primary endpoint is major pathologic response (MPR). We will estimate the MPR rate with a 95% credible interval (CI) assuming that the MPR rate follows a prior beta distribution (0.5, 0.5). For example, if the M7824 monotherapy indeed has a true MPR rate of 30% and 7 patients with MPR are observed in this study, the corresponding 95% CI of the observed MPR rate would be (14.8%, 50.7%). Furthermore, we calculated predictive probability of $\text{Prob}(p > 0.15 \text{data and true MPR rate})$ for a variety of true MPR rates, where p is the MPR rate. As shown in Statistical consideration section in Table 3, there will be a fairly high chance (81 – 89%) for the study to observe a MPR rate > 15% with a sample size of 23 patients if the true MPR rates are 25% and higher. We chose to use 15% MPR rate as cutoff because a historic MPR rate to neoadjuvant chemotherapy alone of 19% is observed (as described by Pataer et al.) (2). However, some patients that receive neoadjuvant chemotherapy may not receive surgery for one reason or another, and these cases will be considered treatment failure. Assuming the 19% major pathologic response rate is calculated from 80% of patients who receive surgery, a conservative estimate of the major pathologic response is 15%.

Analysis of Secondary/Exploratory Endpoints: Analysis for the secondary/exploratory endpoints will be descriptive and exploratory in nature. Descriptive statistics will be provided to summarize the data distribution. Association analysis by Pearson or Spearman correlation coefficient will be calculated for continuous data and chi-square or Fisher's exact test for categorical data. Time-to-event endpoints will be computed using the Kaplan-Meier method.


Toxicity monitoring: A Bayesian method to monitor the toxicity in the perioperative phase will be used. We consider that neoadjuvant therapy with either one of the regimens is not feasible if it results in unacceptable toxicities in at least 20% of the patients with 70% or higher probability. The toxicity monitoring will start after a minimum of 6 patients have

been enrolled. With a prior probability of toxicity as Beta (0.5,0.5), the toxicity stopping boundaries are defined as seeing unacceptable toxicity in ≥ 3 of 6-7, 4 of 8-10, 5 of 11-13, 6 of 14-16, 7 of 17-19, 8 of 20-22 or 9 of 23 patients. When the true toxicity rates are 0.1, 0.3, and 0.5, the probabilities of early stopping are 0.04, 0.56, and 0.97 with the corresponding average sample sizes of 22.4, 15.1 and 8.0, respectively.

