22 STATISTICAL CONSIDERATIONS

This is an open label phase II study with a modular design. Currently, eligible patients will be accrued to the M7824 monotherapy arm (Arm A). The primary objective is to evaluate the rate of MPR, rather than hypothesis testing with pre-specified null and alternative MPR rates. There will be no interim futility nor efficacy monitoring. The primary efficacy endpoint of the study is MPR evaluated in resected tumor tissues following neoadjuvant therapy and defined as $\leq 10\%$ viable tumor cells in the resected specimen using the methods described by Pataer et al. (2).

Analysis of primary efficacy endpoint:

A sample size of 23 patients is proposed for each arm of the study. With an estimated accrual rate of 2-3 patients a month, the accrual period is approximately 15-24 months. We will estimate the MPR rate with a 95% credible interval (CI) assuming that the MPR rate follows a prior beta distribution (0.5, 0.5) with one patient worth of information. For example, if the M7824 monotherapy indeed has a true MPR rate of 30% and 7 patients with MPR are observed in this study, the corresponding 95% CI of the observed MPR rate would be (14.8%, 50.7%).

Furthermore, we calculated predictive probability of $\text{Prob}(p > 0.15 | \text{data and true MPR rate})$ for a variety of true MPR rates, where p is the MPR rate. As shown in the table below (**Table 3**), there will be a fairly high chance (81 – 89%) for the study to observe a MPR rate $> 15\%$ with a sample size of 23 patients if the true MPR rates are 25% and higher.

Table 3. Predictive probabilities of true MPR rates.

True MPR rate	predictive probability of $\text{Prob}(p > 0.15 \text{data and true MPR rate})$ where $a_0=0.5, b_0=0.5$
---------------	--

0.05	12%
0.10	30%
0.15	50%
0.20	67%
0.25	81%
0.30	89%

We chose to use 15% MPR rate as cutoff because a historic major pathologic responserate to neoadjuvant chemotherapy alone of 19% is observed (as described by Pataer et al.) (2). However, some patients that receive neoadjuvant chemotherapy may not receive surgery for one reason or another, and these cases will be considered treatment failure. Assuming the 19% major pathologic response rate is calculated from 80% of patients who receive surgery, a conservative estimate of the major pathologic response is 15%.

Analysis of Secondary/Exploratory Endpoints:

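### The 81–89% given as the chance of observing an MPR rate above 15% is an average posterior probability; the chance of observing it is 86% and 95% at true rates of 25% and 30%

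*Combined protocol and SAP*

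**What the plan says.** The Statistical methods part of the synopsis (Section 1.1) sets the size and the reference value: "A sample size of 23 patients is proposed for the study" and "We chose to use 15% MPR rate as cutoff". The prior on the MPR rate is Beta(0.5, 0.5). The plan then defines what it calculated: a predictive probability of Prob(p > 0.15), given the data and a true rate, with p denoting the MPR rate. Section 22 uses the same definition and prints the results in Table 3, captioned "Predictive probabilities of true MPR rates". The values are 12, 30, 50, 67, 81 and 89% at true rates of 5, 10, 15, 20, 25 and 30%.

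The synopsis reads the last two rows as "a fairly high chance (81 – 89%) for the study to observe a MPR rate > 15% with a sample size of 23 patients". It attaches this claim to every true rate from 25% upwards. Section 22 repeats this: "there will be a fairly high chance (81 – 89%) for the study to observe a MPR rate" above 15%.

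Both places also state that the aim is to estimate the MPR rate, without a formal hypothesis test and without interim efficacy or futility looks.

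**The concern.** The definition and the interpretation describe two different things. A posterior probability that p exceeds 0.15 measures belief about the underlying rate once data are in hand; Table 3 averages it over possible data sets. The chance that the study observes a rate above 15% is a sampling probability for a count of responders. The two need not agree, and the plan gives one set of figures for both.

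Apart from one example credible interval, this sentence is the only quantitative support for 23 patients on the primary endpoint. Section 8.2 says the MPR rate will be set against a historical benchmark, and Section 8.1 makes the next step depend on whether a signal of activity is seen, with no numerical definition of that signal. A reader may therefore treat an observed rate above 15% as informative and look to this sentence for how often it would occur.

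**Working it through.** **Inputs (synopsis and Section 22).** n = 23; prior Beta(0.5, 0.5); cut-off 15%, strictly exceeded; true rates t as listed in Table 3.

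**Step 1: the example interval.** With 7 responders the posterior is Beta(7.5, 16.5). Its 2.5% and 97.5% points are 0.148 and 0.507, matching the printed (14.8%, 50.7%). The prior and sample size are therefore read correctly.

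**Step 2: Table 3.** For x responders the posterior is Beta(x + 0.5, 23.5 − x). The average posterior probability at true rate t is

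A(t) = Σₓ Binomial(x; 23, t) × Pr(p > 0.15 | x), x = 0, …, 23.

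This agrees with all six printed rows to within half a percentage point (third column of the table in Step 4).

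**Step 3: the event the sentence names.** 3/23 = 13.0% and 4/23 = 17.4%, so an observed rate above 15% means X ≥ 4. Its probability is Pr(X ≥ 4) with X ~ Binomial(23, t).

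- At t = 0.25, the probabilities of 0, 1, 2 and 3 responders are 0.0013, 0.0103, 0.0376 and 0.0878. They sum to 0.1370, so Pr(X ≥ 4) = 0.863.
- At t = 0.30, they are 0.0003, 0.0027, 0.0127 and 0.0382. They sum to 0.0538 before rounding, so Pr(X ≥ 4) = 0.946.

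**Step 4: side by side.**

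| True rate | Table 3 | A(t) | Pr(X ≥ 4) | Pr(X ≥ 4) − A(t), points |
|---|---|---|---|---|
| 5% | 12% | 0.120 | 0.026 | −9 |
| 10% | 30% | 0.302 | 0.193 | −11 |
| 15% | 50% | 0.500 | 0.460 | −4 |
| 20% | 67% | 0.674 | 0.703 | +3 |
| 25% | 81% | 0.805 | 0.863 | +6 |
| 30% | 89% | 0.893 | 0.946 | +5 |

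Differences are taken before rounding.

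**Step 5: could another reading give 81% and 89%?**

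- Observed rate taken as the posterior mean, (x + 0.5)/24: 0.146 at x = 3 and 0.188 at x = 4, so the event is still X ≥ 4.
- Posterior Pr(p > 0.15) above one half: 0.42 at x = 3 and 0.65 at x = 4, again X ≥ 4.
- Neighbouring counts: X ≥ 3 gives 95% and 98% at t = 0.25 and 0.30; X ≥ 5 gives 72% and 86%.
- Posterior probability evaluated at the expected count 23t: 0.905 and 0.970.

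Only the average in Step 2 reproduces the table.

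**Step 6: what crossing 15% would show.** At 4/23 the posterior Pr(p > 0.15) is 0.65; at the plan's own example of 7/23 it is 0.97.

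**Step 7: the range of true rates.** The sentence speaks of 25% and above, but 81–89% covers only 25% and 30%. At t = 0.35, A(t) is 0.947 and Pr(X ≥ 4) is 0.982.

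**The case against.** The strongest reply is that the plan contains no wrong calculation. It defines its quantity in the preceding sentence and in the Table 3 column header, computes it correctly, and goes astray only in the verb *observe*. Where the sentence applies, at 25% and above, the literal chance is higher than stated, so the claim of a fairly high chance survives and nobody is led to overrate 23 patients. The plan never reads the rows at 15% and below in this way, so those gaps compare two quantities and are not misstatements in the document. No success rule uses 4/23 or a posterior threshold, and for an estimation study the credible interval is the relevant precision statement.

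Most of this stands. Table 3 is right, the printed figures are conservative at 25% and 30%, and nothing operational depends on them. What does not follow is that the sentence may be left. It names the sample rate, gives probabilities that are wrong for it, and does so twice in the sample-size rationale. Nor is the table a safe stand-in more generally: a reader who takes the sentence's interpretation to the lower rows gets figures that are too high, for example 30% against 19% at a true rate of 10%.

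**Conclusion.** The sentence is wrong as written in both places. It presents an average posterior probability as the chance of an observed result. For the event it names, the figures should be 86% and 95% at true rates of 25% and 30%, a shortfall of 5 to 6 points. Observing more than 15% happens 46% of the time when the true rate equals the 15% reference value, so that result alone separates the drug poorly from the benchmark. The Table 3 caption does not name the tabulated quantity either.

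This is an error of labelling and interpretation with modest effect. Because the design is estimation only, none of these figures is an error rate of a planned rule. The result assumes all 23 patients are in the denominator and that responses are independent with a common true rate, the binomial model under which Table 3 reproduces.

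**What to change.** 1. In the synopsis and in Section 22, replace the sentence with text such as: *The average posterior probability that the MPR rate exceeds 15% is 81% and 89% at true rates of 25% and 30%. The chance of observing an MPR rate above 15% (at least 4 of 23) is 86% and 95% at these rates, and 46% at a true rate of 15%; at 4/23 the posterior probability that the rate exceeds 15% is 0.65.* Naming the two true rates also settles the open-ended range.
2. Retitle Table 3: *Average posterior probability that the MPR rate exceeds 15%, by true MPR rate.*
3. Optionally, add a second column to Table 3 with the chance of at least 4/23: 3, 19, 46, 70, 86 and 95%.

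The first clause of the new sentence and the new caption are enough to correct the error; the rest helps the reader interpret an observed rate just above the benchmark. The cost is one sentence in two places and one caption. The sample size, prior, credible interval and primary analysis are unchanged.

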We consider that neoadjuvant therapy with either one of the regimens is not feasible if it results in unacceptable toxicities in at least 20% of the patients with 70% or higher probability. The toxicity monitoring will start after a minimum of 6 patients have been enrolled with known toxicity outcome. With a prior probability of toxicity as Beta(0.2,0.8), the toxicity stopping boundaries are defined as seeing unacceptable toxicity in ≥ 3 of 6-8, 4 of 9-12, 5 of 13-16, 6 of 17-20 or 7 of 21-23 patients. When the true toxicity rates are 0.1, 0.2, and 0.35, the probabilities of early stopping are 0.06, 0.34, and 0.84 with the corresponding average sample sizes of 22.2, 18.6, and 11.2, respectively. In case one arm needs to be closed due to excessive toxicity, accrual to the remaining arm will continue in a non-randomized way. The calculation was performed using the Shiny Application: Bayesian Toxicity Monitoring version 2.1 (<http://ibl.mdanderson.org/BTM/>).

The Investigator is responsible for completing an efficacy/safety summary report, and submitting it to the IND Office Medical Affairs and Safety Group, for review and approval. This should be

Clinical Study Protocol 9.0
Bintrafusp Alpha- M7824
submitted after the first 6 evaluable patients per study arm, complete 30 days after surgery, and
every 3 evaluable patients per arm, thereafter.

MDA Cancer Center
15 June 2020

A copy of the cohort summary should be placed in the Investigator's Regulatory Binder under
"sponsor correspondence".

24 Data Confidentiality Plan

Confidentiality of Data

All clinical and research information/data will be collected and placed in our institution's Data Management Initiative (DMI) supported by Biostatistical Department under [name] oversight. This is a secured, password-protected intranet-based (UTMDACC only) database. Access to this database is restricted to the PI, protocol research nurse, protocol research data coordinator and DMI database analyst.

The investigator affirms that information as pertains to the study will be maintained in confidence, and such information will be divulged to the IRB, IEC, or similar or expert committee; affiliated institution and employees, only under an appropriate understanding of confidentiality with such board or committee, affiliated institution and employees. Data generated by this study will be considered confidential by the investigator, except to the extent that it is included in a publication.

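### The synopsis and Section 23 give different toxicity stopping rules for the same 20%/70% criterion, and neither boundary table follows from it

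*Combined protocol and SAP*

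**What the plan says.** Both places state one criterion. Section 23 calls the therapy "not feasible if it results in unacceptable toxicities in at least 20% of the patients with 70% or higher probability", and the toxicity monitoring paragraph of the synopsis (Section 1.1) uses the same limit and cut-off. The two accounts then part.

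- **Synopsis.** Prior Beta(0.5,0.5). Stop on "unacceptable toxicity in ≥ 3 of 6-7, 4 of 8-10, 5 of 11-13, 6 of 14-16, 7 of 17-19, 8 of 20-22", then 9 of 23. Stopping probabilities are 0.04, 0.56 and 0.97 at true rates of 0.1, 0.3 and 0.5, with average sample sizes of 22.4, 15.1 and 8.0.
- **Section 23.** Prior Beta(0.2,0.8). Stop on "unacceptable toxicity in ≥ 3 of 6-8, 4 of 9-12, 5 of 13-16, 6 of 17-20 or 7 of 21-23 patients". At true rates of 0.1, 0.2 and 0.35, "the probabilities of early stopping are 0.06, 0.34, and 0.84", with average sample sizes of 22.2, 18.6 and 11.2.

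The synopsis starts monitoring once 6 patients are enrolled; Section 23 requires 6 "enrolled with known toxicity outcome". Section 23 also asks for a safety summary after the first 6 evaluable patients have completed 30 days after surgery, and then after every 3. No text gives either section precedence.

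**The concern.** A single criterion and a single prior determine a single boundary. Two priors and two tables under one criterion cannot both be the rule, and two priors worth one patient each should not by themselves give tables as far apart as 9 of 23 and 7 of 23. That raises a second question: does either table come from the stated criterion at all?

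This is the only formal stopping rule in the trial, since the statistical section excludes interim futility and efficacy monitoring. The events it counts include perioperative death, severe respiratory distress syndrome, broncho-pleural fistula and empyema. If the tables conflict, the same count can mean stop or continue depending on the page consulted. If neither matches the criterion, the trial can carry on past data that the protocol itself describes as showing infeasibility.

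**Working it through.** **Inputs.** Limit 0.20 and cut-off 0.70 (both sections); priors Beta(0.5,0.5) (synopsis) and Beta(0.2,0.8) (Section 23); monitoring from n = 6 to n = 23; the two printed tables.

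**Step 1. Reproduce the printed operating characteristics.** Exact sequential binomial recursion on each printed table, with a look after every patient from n = 6. A first crossing at n = 23 is not counted as early.

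| Table | True rate | P(early stop), computed | Printed | Average n, computed | Printed |
|---|---|---|---|---|---|
| Synopsis | 0.10 | 0.032 | 0.04 | 22.5 | 22.4 |
| Synopsis | 0.30 | 0.554 | 0.56 | 15.2 | 15.1 |
| Synopsis | 0.50 | 0.968 | 0.97 | 8.0 | 8.0 |
| Section 23 | 0.10 | 0.054 | 0.06 | 22.2 | 22.2 |
| Section 23 | 0.20 | 0.337 | 0.34 | 18.6 | 18.6 |
| Section 23 | 0.35 | 0.841 | 0.84 | 11.2 | 11.2 |

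Each set agrees closely with its own table. A misprinted table is therefore unlikely; the operating characteristics describe the rules as printed.

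**Step 2. Derive the boundary from the criterion.** With k events in n patients the posterior is Beta(a + k, b + n − k). The boundary is the smallest k with Pr(p > 0.20 | k, n) ≥ 0.70.

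- Beta(0.5,0.5): 2 of 6-7, 3 of 8-11, 4 of 12-16, 5 of 17-20, 6 of 21-23.
- Beta(0.2,0.8): 2 of 6, 3 of 7-10, 4 of 11-14, 5 of 15-19, 6 of 20-23.

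At the reporting points set by Section 23:

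| n | Synopsis, printed | 20%/70%, Beta(0.5,0.5) | Section 23, printed | 20%/70%, Beta(0.2,0.8) |
|---|---|---|---|---|
| 6 | 3 | 2 | 3 | 2 |
| 9 | 4 | 3 | 4 | 3 |
| 12 | 5 | 4 | 4 | 4 |
| 15 | 6 | 4 | 5 | 5 |
| 18 | 7 | 5 | 6 | 5 |
| 21 | 8 | 6 | 7 | 6 |

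Over all 18 sample sizes:

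- The synopsis table is laxer than its criterion at every one, by 1 event at n = 6 (3 against 2) and by 3 at n = 23 (9 against 6).
- The Section 23 table is laxer by one event at 11 (n = 6, 9, 10, 13, 14, 17-19, 21-23) and agrees at 7.
- The printed tables differ from each other at 13 (n = 8, 11, 12, 14-23).

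**Step 3. Could another cut-off at a 20% limit explain the tables?**

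- Synopsis, Beta(0.5,0.5): 7 of 20 continues at 0.946 while 3 of 7 stops at 0.926. A less extreme posterior stops and a more extreme one continues, so no cut-off produces this table.
- Section 23, Beta(0.2,0.8): the highest posterior that continues is 0.799 (6 of 21), and the lowest that stops is 0.829 (5 of 16). The cut-off must lie above 0.799 and no higher than 0.829. A value of 0.80 reproduces all 18 boundaries; 0.70 does not.

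**Step 4. Particular counts.**

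| Events / n | Pr(p > 0.20), Beta(0.5,0.5) | Pr(p > 0.20), Beta(0.2,0.8) | Synopsis table | Section 23 table |
|---|---|---|---|---|
| 2 / 6 | 0.804 | 0.721 | continue | continue |
| 5 / 18 | 0.801 | 0.752 | continue | continue |
| 6 / 18 | 0.915 | 0.888 | continue | stop |

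**Step 5. Stopping probabilities at common true rates.**

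| Looks | True rate | Synopsis table | Section 23 table | 20%/70%, Beta(0.5,0.5) | 20%/70%, Beta(0.2,0.8) |
|---|---|---|---|---|---|
| Every patient | 0.10 | 0.03 | 0.05 | 0.19 | 0.15 |
| Every patient | 0.20 | 0.22 | 0.34 | 0.59 | 0.53 |
| Every patient | 0.30 | 0.55 | 0.71 | 0.87 | 0.84 |
| Every patient | 0.35 | 0.72 | 0.84 | 0.94 | 0.92 |
| n = 6, 9, …, 21 | 0.20 | 0.17 | 0.27 | 0.51 | 0.48 |
| n = 6, 9, …, 21 | 0.30 | 0.47 | 0.64 | 0.82 | 0.80 |
| n = 6, 9, …, 21 | 0.35 | 0.64 | 0.79 | 0.91 | 0.90 |

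**The case against.** The best defence is that the synopsis only summarises. Section 23 holds the definition of unacceptable toxicity, the software and the reporting schedule, so staff would probably work from it, and its table misses the stated criterion by no more than one event. The sponsor may also have wanted the laxer boundaries: at a true rate of 10%, the stated criterion would stop early with probability 0.15 to 0.19, against 0.03 to 0.05 for the printed tables.

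Part of this stands. Section 23 is closer to its criterion than the synopsis is, and its printed operating characteristics are sound for its own table. The difference in when monitoring starts is probably shorthand, because a boundary that counts events needs known outcomes.

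The defence does not remove the problem. No text makes Section 23 govern, and Section 23 contradicts its own 70%. One event matters at these sizes: the first scheduled report is at n = 6, where 2 events meet the criterion under either prior and both tables continue. If laxer boundaries were intended, the criterion sentence is wrong in both places. Looking only at the scheduled reports does not help either, since the tables differ from each other at four of the six (n = 12, 15, 18 and 21).

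**Conclusion.** The concern holds. The plan contains two incompatible stopping rules, and neither is the rule that its criterion describes; both are laxer. At a true rate of 20%, with a look after every patient, the tables stop early with probability 0.22 and 0.34, while the stated criterion would do so with probability 0.59 or 0.53 depending on the prior. The gap remains with looks at 6 and then every 3 patients.

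The figures assume that the boundary is the smallest count meeting the posterior condition; whether the limit is read as at least 20% or above 20% makes no difference for a continuous posterior. The boundary mismatch does not depend on the look schedule; only the stopping probabilities do. The 20%/80% match for Section 23 is not the only limit and cut-off pair that fits, so it does not establish what was intended. Nothing here says which limit, cut-off or table is right. This must be fixed before the rule can be relied on.

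**What to change.** Reconcile the synopsis and Section 23. The sponsor should choose one prior, one toxicity limit, one probability cut-off and one look schedule, and carry Section 23's requirement of known outcomes for the first 6 patients into the synopsis if that is what is meant. The boundaries and operating characteristics should then be regenerated from those inputs, at one set of true rates and for the looks that will actually take place, and stated identically in both sections. The printed figures match a look after every patient, whereas the reports are due at 6 and then every 3.

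Copying the present Section 23 text into the synopsis would not be enough, because its table does not match its stated 70%. Changing only the synopsis limit would leave the two sections in conflict.

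The cost is one rerun of the monitoring software already named in Section 23, and matching wording in an amendment.
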